In accordance with ICH/GCP reporting guidelines and ISO/DIS 14155 draft standard, Adverse Events (AEs), Serious Adverse Events (SAEs), Adverse Device Effect (ADEs), Serious Adverse Device Effect (SADEs), and Unanticipated Serious Adverse Device Effect (USADEs) will be collected and recorded throughout the duration of the trial. The investigator and facility should report all AEs, SAEs, which are not device attributed in line with facilities internal adverse event reporting procedures.

The investigator *should not* report device attributed events without prior consultation with the study's Medical Monitor. The investigator is also responsible for ensuring that all AEs and SAEs are recorded on the Adverse Event Log and all reportable ADEs (ADEs, SADEs, USADEs) are recorded and reported to the Sponsor in accordance with instructions in this section.

Device attributed adverse events, device attributed serious adverse events and device attributed unexpected adverse events will be reported by the Sponsor of the clinical trial in line with current FDA regulatory requirements.

Definitions for safety reporting purposes in this trial are as follows:

[figure not shown]
- **Adverse Event:** Any untoward medical occurrence in a subject or clinical investigation which does not necessarily have a causal relationship with the medical device under investigation.
- Serious Adverse Event: An adverse event that results in one of the following outcomes: requires
 hospitalization; prolongs hospitalization; is life-threatening; results in congenital anomaly/birth defect;
 results in death.

Study Number IRR-CT-901-2013-01	Version: 1.0	01AUG2014
© Confidential IrriMax Corporation		Page 22 of 35

- Adverse Device Effect: An adverse event that results from the presence or performance of the device or any component of the system.
- **Serious Adverse Device Effect:** An adverse event related to the presence or performance of the device or any component of the system that results in one of the following outcomes: requires hospitalization; prolongs hospitalization; is life-threatening; results in congenital anomaly/birth defect; results in death.
- Serious Unexpected Device Effect: Any serious adverse effect on health or safety or any lifethreatening problem or death caused by, or associated with, a device, if that effect, problem, or death was not previously identified in nature, severity, or degree of incidence in the investigational plan or application, or any other unanticipated serious problem associated with a device that related to the rights, safety, or welfare of subject.

The Decision Tree in Figure 1 below is an adaptation of Annex F of the 2009 ISO/DIS draft standard and can be used to differentiate the adverse events for this trial. Detailed information as to how to this decision tree will be used and how adverse events will be reported can be found in the study reference binder.

Figure 1. Decision Tree for Classification of Adverse Events [21]

Reporting of Adverse Events

Reporting of Adverse Events (AEs) and Serious Adverse Events (SAEs) begins as soon as a subject signs consent. Reporting of device related Adverse Events will begin at the Perioperative Phase (when the study device is employed). All subjects will be closely monitored and questioned regarding the occurrence of AEs. AEs must be documented on an AE Log and on the CRF as appropriate. If no AEs have been observed for a subject during the course of the study this must also be clearly indicated on the AE page of the CRF and documented in the subject's source documentation. SAEs must be additionally documented. For each AE or SAE, the following information will be recorded:

- Identified AE/SAE (e.g. erythema)
- Start/Stop Time and Date of AE/SAE
- Severity
- Action taken for the event

- Duration of AE/SAE
- Relationship to Study Product
- Outcome
- Level of Seriousness

All AEs and SAEs must be treated in accordance with established standards of medical care. In recording AEs and SAEs the diagnosis, if known, is preferred rather than a listing of signs and symptoms. The onset or start of the AE/SAE should be the time and date that the symptoms started medical condition/disease present prior to the subject starting the study and that has worsened during study participation. The onset or start time and date of AEs or SAEs secondary to the worsening of a pre-existing condition should be the time and date on which the condition was known to have worsened.

Methods and Timing for Capturing and Assessing Safety Parameters

For each AE, including SAEs, and ADE, including SADE and USADE ("Adverse Event") the investigator will make assessment of seriousness, severity, and causality.

Adverse Event Documentation

Investigators will seek information on adverse events at each patient contact. All AEs, whether reported by the patient or noted by study personnel, will be recorded in the patient's source document and on the Adverse Event Log.

Assessment of Causality of Adverse Events

Investigators should use their knowledge of the patient, the circumstances surrounding the event, and an evaluation of any alternative causes to determine whether or not an AE is considered to be related to the study product, indicating a "yes" or "no" accordingly. The following guidance should be taken into consideration:

- Temporal relationship of event onset to the initiation of study product
- Course of the event, considering especially the effects of anesthesia and surgery
- Known association of the event with the study product or with similar treatments
- Known association of the event with the surgical interventions under study
- Presence of risk factors in the patient or use of concomitant medications known to increase the
 occurrence of the event

Procedures for Recording Adverse Events

Investigators should use correct medical terminology/concepts when recording AEs on the Adverse Event CRF. Avoid colloquialisms and abbreviations.

Study Number IRR-CT-901-2013-01	Version: 1.0	01AUG2014
© Confidential IrriMax Corporation		Page 24 of 35

Only one AE term should be recorded in the event field on the Adverse Event CRF.

Adverse Events Occurring Secondary to Other Events

In general, AEs occurring secondary to other events (e.g., cascade of events or clinical sequelae) should be identified by their primary cause, with the exception of severe or serious secondary events. However, medically significant AEs occurring secondary to an initiating event that are separated in time should be recorded as independent events on the Adverse Event CRF.

Persistent or Recurrent Adverse Events

A persistent AE is one that extends continuously, without resolution, between patient evaluation time points. Such events should only be recorded once on the Adverse Event CRF. The initial severity of the events should be recorded, and the severity should be updated to reflect the most extreme severity any time the event worsens. If the event becomes serious, the Adverse Event CRF should be updated to reflect this.

A recurrent AE is one that resolves between patient evaluation time points and subsequently recurs. Each recurrence should be recorded separately on the Adverse Event CRF.

Abnormal Vital Signs

Not every vital sign abnormality qualifies as an adverse event. A vital sign result should be reported as an AE if it meets any of the following criteria:

- Results in a change in study product treatment (treatment interruption)
- Clinically significant in the investigator's judgment

It is the investigator's responsibility to review all vital sign findings. **Medical and scientific judgment should** be exercised in deciding whether an isolated vital sign abnormality should be classified as an AE.

Deaths

All deaths that occur during the protocol-specified AE reporting period, regardless of relationship to study product, must be recorded on the Adverse Event CRF and immediately reported to the Sponsor.

Death should be considered an outcome and not a distinct event. The event or condition or condition that contributed to the fatal outcome should be recorded as the single medical concept on the Adverse Event CRF. The term "sudden death" should only be used for the occurrence of an abrupt and unexpected death due to presumed cardiac causes, pulmonary embolus (air embolus or fat embolus), or catastrophic stroke, in a patient without preexisting cardiac disease or history of TIA or stroke, within one hour of onset of acute symptoms, or in the case of unwitnessed death, within 24 hours of when the patient was last seen alive and stable.

Preexisting Medical Conditions

A preexisting medical condition is one that is present at the screening visit for this study. Such conditions should be recorded on the CRF.

Immediate Reporting Requirements from Investigator to Sponsor

Certain events require immediate reporting to allow the Sponsor to take appropriate measures to address potential new risks in a clinical trial. The investigator must report such events to the Sponsor immediately using the toll free number [contact] and in writing using the ADE Report Form via email [contact] or fax using the toll free number [name], under no circumstance should the reporting take place more than 18 hours after the investigator learns of the event. All device attributed events will require review and discussion with the Investigator and Medical Monitor.

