• To compare the rate of SSI in the IrriSept system randomization group to the rate of SSI in Standard of Care randomization group.

Secondary Objective(s):

- To compare the hospital readmission rate of subjects receiving the IrriSept system to the hospital readmission rate of subjects receiving Standard of Care treatment.
- To compare the estimated hospital cost to charge ratio between the IrriSept system and Standard of Care.
- To compare the length of hospital stay between IrriSept system and Standard of Care.

Study Product:

Product Name: IRRISEPT[™] Wound Debridement and Cleansing System

Registration Number: 3005706359

Product Status: Active

Registered Company: IrriMax Corporation

IrriSept system containing sterile 0.05% Chlorhexidine Gluconate (CHG) in water for irrigation, USP (99.95%), and sterile 0.9% normal saline packaged with 2 sterile IrriProbes, packaged for study use as a "kit". Two (2) complete "kits" will be used per the study specific IFU (Instructions for Use) for each subject randomized to Study Product.

Study Design:

This is a randomized, open-label, parallel-group study. The study consists of 3 parts: a Screening Phase typically performed in the Emergency Department, a randomized, open-label Treatment (Perioperative) Phase, and End of Study, a 30-day Follow-up.

Study Number IRR-CT-901-2013-01	Version: 1.0	01AUG2014
© Confidential IrriMax Corporation		Page 10 of 35

Study Sample Size:

1100 screened, approximately 650 completed, 600 evaluated

Study Background:

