- Subjects randomized to Standard of Care will receive surgical wound irrigation at the discretion of the investigator.
- Use of the IrriSept system will be documented using the organization's standard medical and nursing records (e.g. the surgeons operative report, OR nursing record, anesthesia record, charge master) in subjects who are randomized to this treatment group.

Visit 1: Post-Surgical Assessments

The first assessments are completed immediately after the subject is admitted to the post-operative area. Post-Surgical Assessments include:

- Complete Procedure related questions
 - Location of surgical site incision
 - If drains were used during the procedure and the location(s)
 - If the subject experienced hypothermia during the procedure
 - Type of surgical skin preparation used during the procedure
 - Type of skin closure used during the procedure
 - Confirmation the surgery resulted in primary closure
- Complete remaining appropriate assessment scales
 - Primary injury notation and score (complete appropriate/applicable scale*):
 - Blunt Trauma Score*, or
 - Penetrating Abdominal Trauma Index (PATI)*, or
 - Acute Abdomen Surgery Index*

Study Number IRR-CT-901-2013-01	Version: 1.0	01AUG2014
© Confidential IrriMax Corporation		Page 20 of 35

Other Instructions

The following activities are also required to be recorded, per incident, on study specific logs in the CRF and/or documented in source:

- Adverse Events (AEs), Serious Adverse Events (SAEs), Adverse Device Effects (ADEs), Serious Adverse Device Effects (SADEs) and Unanticipated Serious Adverse Device Effects (USADEs)
- Dispensing and accountability of the investigational device kits
- Recording of Protocol Deviations

Visit 2: End of Study

All study subjects will be scheduled to attend Visit 2, which is 30-days post index procedure (+/-3 days) visit. If a subject is not able to attend Visit 2, a designated research staff member may conduct as many assessments as possible, by telephone, and complete the CRF as appropriate. If a subject was seen for a Standard of Care (SoC) follow-up visit prior to the study specific Visit 2, and is not able to attend the Visit 2, data collected at the SoC visit should be referenced during the Visit 2 phone call and on the Visit 2 CRF.

If the subject has expired prior to Visit 2, the site must complete as much of the CRF as possible.

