This section outlines the statistical analysis strategy and procedures for the study. If, after the study has begun, changes are made to primary and/or key secondary hypotheses, or the statistical methods related to those hypotheses, then the protocol will be amended (consistent with ICH Guideline E-9). Changes to exploratory or other non-confirmatory analyses made after the protocol has been finalized, along with an explanation as to when and why they occurred, will be listed in the Clinical Study Report (CSR) for the study. Post hoc exploratory analyses will be clearly identified in the CSR. A separate Statistical Analysis Plan (SAP) with further details than presented here will be finalized prior to first patient enrolled to minimize any bias, as the study is non-blinded.

Power and Sample Size

The determination of sample size for this study is based on the primary objective to demonstrate the superiority of the IrriSept irrigation unit versus conventional standard of care in patients who undergo open abdominal laparotomy for abdominal trauma or acute surgical abdomen within 36 hours of initial presentation to their healthcare organization. The primary endpoint is the rate of SSI observed within 30 days (+/- 3 days) from the date of the index operation.

Based on historical data, it is assumed that the rate of SSI within the standard of care group will be \geq 20%. A total of 600 patients (300 per group) will provide \geq 90% power to demonstrate a reduction in the rate of SSI, up to 50%, assuming a control group rate for SSI of \geq 20%, based on a two-sided Chi-square test with a 5% significance level. The following table shows the power achieved under various combinations of control group SSI rates and relative treatment differences.

Table 2.1: Power associated with a total sample size of 600 (n=300/group), based on a two-sided Chi-square test with a 5% significance level.

Control Group SSI	Relative Treatment Difference (IrriSept/Control)		
Rate	50% Reduction	40% Reduction	30% Reduction
15%	83%	62%	38%
20%	93%	76%	50%
25%	98%	87%	61%

It is anticipated that approximately 1100 patients will be screened, 650 patients will be enrolled, to obtain 600 evaluable patients, based on a non-evaluable rate of approximately 5%. All calculations were carried out in SAS version 9.2 using the comparison for two independent proportions procedure in PROC POWER.

Study Number IRR-CT-901-2013-01	Version: 1.0	01AUG2014

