© Confidential IrriMax Corporation		Page 28 of 35

Analysis Populations

Intention-to Treat (ITT)

The intention-to-treat population will be defined as all randomized subjects. Subjects will be assigned to a group based on the group they were randomized to.

Per-Protocol Population (PP)

Within the ITT population, subjects will be considered evaluable if they completed the 30 day follow up visit. Subjects who are withdrawn from the study prior to the 30 day follow up will be designated "non-evaluable" and excluded from the PP population.

Safety Analysis Set (SAS)

The safety analysis set will consist of all randomized subjects who underwent an emergency operation. The safety analysis set will be used for all safety analyses. Subjects will be assigned to a group based on the actual procedure received.

Efficacy Analyses

Primary Endpoint

For the primary endpoint, the number and proportion of patients with a SSI observed within 30 days from the date of emergency operation will be summarized by treatment group, along with the difference and 95% confidence interval for the difference (based on the Wald method). If a patient is missing their end of study assessment, or if they died prior to the end of study assessment, they will be classified as having met the primary endpoint of a SSI. A comparison between treatment groups will be made using the Cochran-Mantel-Haenszal test, stratified by site. The two-sided p-value, the adjusted relative risk (IrriSept/Control) and 95% confidence interval of the relative risk (based on the Wald method) will be reported. The study will be deemed successful if the two-sided p-value for the end of study treatment difference is < 5%.

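### Telephone assessment of Visit 2 non-attenders is optional and its status undefined, so site calling effort can decide how, or whether, a subject counts in the primary endpoint

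*Combined protocol and SAP*

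**What the plan says.** Visit 2: End of Study fixes the time point: "All study subjects will be scheduled to attend Visit 2, which is 30-days post index procedure (+/-3 days) visit". For those who do not come, it says: "If a subject is not able to attend Visit 2, a designated research staff member may conduct as many assessments as possible, by telephone". If such a subject had an earlier routine clinic visit, "data collected at the SoC visit should be referenced during the Visit 2 phone call and on the Visit 2 CRF". The section gives no number of attempts, call window, set of SSI questions or general record check. In Table 3 the presence of SSI is assessed only at Visit 2.

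Three places in the statistical section depend on whether that contact took place:

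- Primary Endpoint: "If a patient is missing their end of study assessment, or if they died prior to the end of study assessment", then "they will be classified as having met the primary endpoint of a SSI".
- Per-Protocol Population: "subjects will be considered evaluable if they completed the 30 day follow up visit".
- Disposition: subjects who withdraw or do not complete the End of Study visit are non-evaluable, their data are kept out of the final efficacy analysis, and they are replaced as needed to reach 600 evaluable.

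None of the three says whether a telephone contact qualifies. On blinding, the Study Summary says "This is a randomized, open-label, parallel-group study", and Statistical Methods says the separate SAP will be finalized early "to minimize any bias, as the study is non-blinded". No blinded assessor or adjudication of SSI is described.

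**The concern.** The Visit 2 contact produces the primary endpoint. For a non-attender, the text leaves both the decision to telephone and the persistence of the attempt to site staff. Two subjects with the same infection-free course can then enter the analysis differently only because one was called.

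Two things are at stake. Low effort, even if equal in both arms, adds imputed SSIs to both arms and dilutes a real effect. Unequal effort creates a difference between arms with no difference in infection. The second is the usual worry in an open-label trial, and the plan has no feature aimed at it.

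**Working it through.** **1. How an infection-free non-attender is handled**

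| Situation | Primary Endpoint rule | Disposition rule |
|---|---|---|
| Reached, and the contact counts | No SSI | Analysed, no SSI |
| Reached, but the contact does not count | SSI | Excluded and replaced |
| Not called or not reached | SSI | Excluded and replaced |

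The documents do not say which row applies to a reached subject, or which column governs.

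**2. Reproducing the planned power**

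Inputs from Power and Sample Size: 300 per group, 20% v 10%, two-sided 5% chi-square. With a pooled proportion of 0.15:

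- SE under the null = √(2 × 0.15 × 0.85 / 300) = 0.02915
- SE under the alternative = √((0.20 × 0.80 + 0.10 × 0.90) / 300) = 0.02887
- z = (0.10 − 1.96 × 0.02915) / 0.02887 = 1.48, so power is 93.1%. Table 2.1 gives 93%.

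**3. Nobody called, Primary Endpoint rule**

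Let m be the share not attending. The documents give no such figure; 5% and 10% are assumed. The observed rate is p + (1 − p) × m.

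- m = 5%: 0.20 + 0.80 × 0.05 = 24.0%; 0.10 + 0.90 × 0.05 = 14.5%; power 84.1%
- m = 10%: 0.20 + 0.80 × 0.10 = 28.0%; 0.10 + 0.90 × 0.10 = 19.0%; power 74.0%

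**4. Unequal reach with no true effect, Primary Endpoint rule**

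The spurious difference is m × (difference in reach) × (1 − p). Reach rates, m and p = 15% are all assumptions. The rejection rates take 15% true SSI in everyone and 300 per arm, and use an unstratified chi-square in place of the planned site-stratified Cochran-Mantel-Haenszel test.

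| Non-attendance | Reach by arm | Spurious difference | Two-sided rejection (nominal 5%) |
|---|---|---|---|
| 10% | 90% v 80% | 0.10 × 0.10 × 0.85 = 0.85 points | 5.9% |
| 30% | 90% v 80% | 0.30 × 0.10 × 0.85 = 2.55 points | 12.6% |
| 30% | 95% v 80% | 0.30 × 0.15 × 0.85 = 3.8 points | 22.8% |

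If attenders have a 20% SSI rate and non-attenders 15%, the three rejection rates are about 5.8%, 12% and 21%. The planned difference is 10 points. The error favours whichever arm is better reached.

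**5. Disposition rule**

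Here calling decides who is in the analysed set. Replacement restores the number, so the power loss in step 3 does not arise. The risk is selection, whose size depends on how non-attenders' SSI rate differs from attenders'. The documents give no basis for a figure.

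**The case against.** The strongest reply is that the section itself speaks of a Visit 2 phone call as an expected step, so the permissive verb may only allow telephone in place of attendance. Call schedules are also operational detail that could sit in the separate SAP, the CRF completion guidelines or the study reference binder, none of which was available here. That is fair on the number and timing of calls. It does not settle whether a call counts as the assessment, or which of the two missing-data rules applies; both belong in the analysis text and are open there.

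Four stronger readings are tempting, and the documents do not support them:

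- *Every uncalled non-attender becomes an SSI.* This is only one of two conflicting rules; Disposition would exclude and replace the subject.
- *A telephone result is pure self-report.* Earlier clinic data are to be referenced where they exist, and Visit 2 also documents readmissions, cultures if an SSI is documented, and antibiotics. Earlier clinic data, however, speak only to the period up to that visit.
- *Staff know the arm and would call unequally.* The text says only that the caller is a designated research staff member. Open-label conduct makes knowledge of the arm likely, but no passage states it or suggests unequal effort.
- *The planned analyses would hide the problem.* Completion and early discontinuation are reported by arm. In the three scenarios of step 4 the unreached shares are 1% v 2%, 3% v 6% and 1.5% v 6% of the arm, an imbalance such a table would partly show. It would not show the mode of contact among those reached.

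**Conclusion.** The point holds as a gap in ascertainment and in the definition of assessed status. Followed as written, discretionary calling decides either between an observed result and an imputed SSI, or between inclusion and exclusion with replacement.

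Under the imputation rule, the power loss from calling nobody is material at modest non-attendance and needs no biased behaviour. The false-positive risk from unequal reach runs from negligible at 10% non-attendance to material at 30%. All of this rests on assumed non-attendance and reach rates; the nearest figure in the plan is its non-evaluable allowance of about 5%, which is not a non-attendance rate. The change is worth making because it is cheap and protects the primary endpoint, not because bias has been shown.

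**What to change.** - **Visit 2: End of Study.** Require, identically in both arms, a fixed minimum number of call attempts within the day-30 window, with standard SSI questions, plus a medical-record check for every non-attender.
- **Primary Endpoint, Per-Protocol Population and Disposition.** State that SSI status obtained by telephone or chart counts as assessed only if it covers follow-up to day 30 (±3 days), or if an SSI is already documented. The date condition stops an early clinic note from standing in for 30-day status.
- **Primary Endpoint and Disposition.** Reconcile SSI imputation with exclusion and replacement, so that one rule governs the primary analysis.
- **Reporting.** Record the mode of assessment, and tabulate mode and unreached subjects by arm. Add a sensitivity analysis that treats telephone-only SSI status as missing, with the handling of those missing values stated in advance.

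A fixed rule removes discretion over whether to call; it does not remove the caller's likely knowledge of the arm, which is why the standard questions and the by-arm table are needed.

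The cost is protocol wording, a few more calls and record checks by existing staff, one CRF field, one table and one sensitivity analysis. Treatment and sample size do not change.
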